Study Protocol

Intraoperative Pain During Carpal Tunnel Release: WALANT vs Local Anesthesia and Tourniquet – A Randomized Controlled Trial

1. Administrative information

- **Protocol Version:** 1.0 (Final), dated 10 October 2024.
- **Principal Investigator (PI):**
 - [name] [name], PhD
 - Associate Professor of Orthopedic Surgery
 - Faculty of Medicine, Misr University for Science and Technology, Giza, Egypt
- **Co-Investigators:**
 - [name] [name], PhD – Assistant Professor of Neurosurgery, Al-Azhar University, Cairo, Egypt
 - Others as per authorship list ([name], [name], [name]).
- **Study Sites:**
 - Site 1: Department of Orthopedic Surgery, tertiary university hospital, Giza, Egypt.
 - Site 2: Department of Neurosurgery, tertiary university hospital, Cairo, Egypt.
- **Regulatory / Ethics Approvals:**
 - Approved by institutional review board/ethics committee at participating centers prior to enrollment.
 - Conducted according to the Declaration of Helsinki and CONSORT 2025 RCT reporting guidance.
- **Funding:**
 - No external funding.

2. Background and rationale

Carpal tunnel decompression (CTD) is one of the most common hand procedures, with several anesthetic options including local anesthesia with pneumatic tourniquet (LA-T), regional block, and general anesthesia. Tourniquet use can cause significant pain, anxiety, and potential complications without proven long-term functional benefit.

Wide-awake local anesthesia no tourniquet (WALANT) uses lidocaine with epinephrine to achieve field anesthesia and vasoconstriction, avoiding tourniquet and sedation, while allowing intraoperative functional assessment and potentially reducing costs and turnaround time. Prior RCTs and observational studies suggest lower perioperative pain and similar complication rates with WALANT, but many are limited by small sample size, non-blinded designs, and single-surgeon experience.

This trial was designed as a multicenter, prospective, double-blinded randomized controlled study to provide high-quality evidence comparing WALANT versus LA-T for intraoperative pain and related outcomes in CTD.

3. Objectives and hypotheses

Primary Objective

To compare intraoperative pain during open carpal tunnel decompression performed under WALANT versus LA-T in adult patients with carpal tunnel syndrome.

Secondary Objectives

- To compare pain during local anesthetic infiltration between WALANT and LA-T.

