- To assess tourniquet-specific pain in the LA-T group.
- To compare operative time between groups.

- To compare patient satisfaction with the operating-room experience.
- To describe intraoperative complications in each group.

Primary Hypothesis

WALANT will result in significantly lower overall intraoperative pain (VAS) than LA-T.

Secondary Hypotheses

- Infiltration pain will be similar between WALANT and LA-T.
- Tourniquet pain will contribute to higher intraoperative pain in LA-T.
- WALANT will shorten operative time compared with LA-T.
- Patient satisfaction will be high and not inferior in WALANT compared with LA-T.

4. Study design

Prospective, multicenter, double-blinded, randomized controlled trial with two parallel arms (1:1 allocation). Patients were randomized to WALANT or LA-T and followed through the perioperative period until early postoperative assessment.

- **Study Type:** Interventional, treatment.
- **Interventional Model:** Parallel assignment, two arms.
- **Masking:**
 - Patients and outcome assessors: blinded to group allocation.
 - Surgeons and anesthetic personnel: aware of technique for safety; allocation concealed until after consent and randomization.

5. Study setting and timeline

- **Sites:**
 - Tertiary academic orthopedic and neurosurgical departments in Giza and Cairo, Egypt.
- **Study Period:**
 - Enrollment and follow-up from December 2024 to December 2025.

6. Eligibility criteria

Inclusion Criteria

- Age ≥ 18 years.
- Clinical diagnosis of carpal tunnel syndrome confirmed by nerve conduction and electromyographic studies.
- Candidate for surgical treatment with open carpal tunnel decompression.
- American Society of Anesthesiologists (ASA) physical status I or II.
- Ability to provide written informed consent.

Exclusion Criteria

- Surgery-related anxiety requiring sedation or general anesthesia.
- Known contraindication or allergy to lidocaine or epinephrine.

- Active local or systemic infection at the surgical site.
- ASA physical status III or higher.
- Pregnancy or breastfeeding.
- Inability to understand or complete pain and satisfaction scales, or to provide informed consent.

7. Interventions

Arm A – WALANT

- 20 mL of 1% lidocaine (200 mg) with epinephrine 1:100,000, buffered with 8.4% sodium bicarbonate (10:1 ratio).
- Infiltrated into the operative field approximately 20 minutes before incision in a preoperative area.
- No tourniquet used.

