- Mini-open carpal tunnel release through a 2–3 cm incision in a minor procedure room, under full aseptic technique; hemostasis via epinephrine-induced vasoconstriction and meticulous technique.

Arm B – Local Anesthesia With Tourniquet (LA-T)

- 20 mL of 1% lidocaine (200 mg) buffered identically but without epinephrine.
- Infiltrated approximately 5 minutes before incision in the operating room.
- A blood-pressure cuff tourniquet placed above the elbow (no exsanguination), inflated to 100 mmHg above systolic pressure after arm elevation and draping, released after skin closure.
- Mini-open carpal tunnel release through a 2–3 cm incision under standard aseptic conditions.

Two experienced surgeons (orthopedic hand consultant and neurosurgery peripheral nerve specialist) performed all procedures; each performed approximately 50 cases.

8. Outcomes

Primary Outcome

- Overall intraoperative pain (VAS 0–10): patient's rating of pain during the entire surgery, assessed immediately after surgery by a blinded assessor.

Secondary Outcomes

- Infiltration pain (VAS 0–10): pain during local anesthetic injection.
- Tourniquet pain (VAS 0–10): tourniquet-specific pain in LA-T group.
- Operative time (minutes): from skin incision to completion of skin closure.
- Patient satisfaction (0–10 scale): global satisfaction with the operating-room experience.
- Intraoperative complications: bleeding requiring intervention, nerve injury, or other deviations from normal course.

Demographics: age, sex, BMI, ASA class, CTS-6 severity score.

9. Sample size

A target sample of 100 patients (50 per arm) was chosen based on feasibility at the two centers and expected medium effect size in intraoperative pain VAS. Post-hoc analysis showed that with 50 participants per group and the observed

effect size (Cohen's $d \approx 0.75$), power was approximately 94% (two-sided $\alpha = 0.05$) to detect the group difference in intraoperative pain.

10. Randomization and allocation concealment

- Simple computerized randomization with 1:1 allocation to WALANT or LA-T.
- Randomization list held by an investigator ([name]) not involved in surgery or postoperative assessment.
- On the day of surgery, the investigator informed the operating surgeon of the assigned technique after consent, maintaining concealment before enrollment.

11. Blinding

- Patients were not explicitly told which anesthetic technique they received.

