- Outcome assessors (who collected VAS and satisfaction scores) were independent and blinded to group assignment.
- Surgical team necessarily aware of technique; however, standardized perioperative communication and identical questionnaires minimized performance bias.

12. Data collection and management

- Standardized questionnaire completed postoperatively by the patient and a blinded assessor captured VAS scores, satisfaction, and complications.
- Operative time and tourniquet parameters abstracted from operative notes.
- Data were entered into a secure, password-protected electronic spreadsheet; quality checks performed for range and consistency.

13. Statistical considerations

See separate SAP (Section B). Briefly, continuous variables were summarized as mean \pm SD or median (IQR) depending on distribution; categorical variables as counts and percentages. Intraoperative VAS (primary outcome) was compared using Mann–Whitney U test; subgroup analyses by age, sex, and surgeon were pre-specified.

14. Ethical considerations

- Approved by IRB/ethics committee at participating institutions.
- All participants provided written informed consent before randomization.
- Risks: injection pain, tourniquet discomfort (LA-T), bleeding, infection, nerve injury, allergic reaction, cardiovascular effects of epinephrine; these are standard risks of hand surgery and local anesthesia.
- Benefits: potential for improved intraoperative comfort; contribution to knowledge that may improve anesthetic choices for future patients.
- Confidentiality: data stored with coded IDs; no identifying information in reports or publications.

B. Statistical Analysis Plan (SAP)

Study: WALANT vs Local Anesthesia With Tourniquet for Carpal Tunnel Decompression – Randomized Controlled Trial

1. Objectives and endpoints

Primary Endpoint

- Overall intraoperative pain VAS (0–10).

Secondary Endpoints

- Pain during anesthetic infiltration (VAS 0–10).
- Tourniquet pain in LA-T group (VAS 0–10).
- Operative time (minutes).
- Patient satisfaction score (0–10).
- Intraoperative complications (yes/no; type).

2. Analysis populations

- **Intention-to-Treat (ITT) Population:**
All randomized participants analyzed according to allocated group, regardless of minor protocol deviations, provided primary outcome data are available.
- **Per-Protocol (PP) Population (exploratory):**

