- Analysis: counts and proportions in each group; Fisher’s exact or chi-square test if sufficient events.
- Given low expected event counts, analysis is primarily descriptive.

Multiplicity:

Secondary outcomes are interpreted cautiously; no formal adjustment for multiple comparisons. Emphasis remains on the primary outcome.

7. Subgroup analyses

Pre-specified subgroups:

- Age group: <65 vs ≥65 years.
- Sex: male vs female.
- Surgeon: Orthopedic (Surgeon A) vs Neurosurgery (Surgeon B).

For each subgroup:

- Compare intraoperative VAS between WALANT and LA-T using Mann–Whitney U test within strata.
- Test for interaction (e.g., using non-parametric interaction tests or rank-based methods) to assess whether the treatment effect differs by age, sex, or surgeon; manuscript reported non-significant interactions (age p=0.45, sex p=0.82, specialty p=0.76).

Subgroup findings are exploratory and hypothesis-generating.

8. Handling of missing data

- Missing primary outcome data are expected to be rare because VAS is collected immediately postoperatively.
- If isolated missing VAS values occur, primary analysis will be complete-case (excluding those without any intraoperative VAS value). Given small numbers, imputation is unlikely to materially change results.
- If >5% of participants lack primary outcome data, a sensitivity analysis using simple imputation (e.g., median of group) may be explored, but the main report will transparently present complete-case results.

9. Sensitivity and additional analyses

- **Timing of anesthetic administration:**
Exploratory analyses to assess whether variation in injection-to-incision time confounds results; previous sensitivity analysis showed no meaningful pattern.
- **Post-hoc power:**
Based on observed effect (mean 0.80 vs 2.08, pooled SD 1.52), Cohen's $d \approx 0.75$, and $n=50$ per group, post-hoc power $\approx 94\%$ ($\alpha=0.05$).
- **Graphical displays:**
Box plots and distribution plots for VAS scores, operative time, and tourniquet pain; subgroup plots by age, sex, and surgeon.

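### As written, infiltration pain is rated only after an operation that differs by arm, so recall can bias the between-arm comparison of injection pain

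*Combined protocol and SAP*

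**What the plan says.** Comparing injection pain between the arms is the first secondary objective in Protocol Section 3: "To compare pain during local anesthetic infiltration between WALANT and LA-T". The matching hypothesis is "Infiltration pain will be similar between WALANT and LA-T", with no margin given. SAP Section 6 (item 1) tests the outcome with an unadjusted Mann–Whitney U test.

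Protocol Section 8 defines the outcome as "Infiltration pain (VAS 0–10): pain during local anesthetic injection" and stops there. The primary outcome in the same section does carry a rating time: "patient's rating of pain during the entire surgery, assessed immediately after surgery by a blinded assessor". Protocol Section 12 describes how the scores reach the database: "Standardized questionnaire completed postoperatively by the patient and a blinded assessor captured VAS scores, satisfaction, and complications". SAP Section 8 says that "VAS is collected immediately postoperatively", although that sentence concerns the primary outcome.

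The injection itself is timed and placed differently by arm in Protocol Section 7. For WALANT: "Infiltrated into the operative field approximately 20 minutes before incision in a preoperative area". For LA-T: "Infiltrated approximately 5 minutes before incision in the operating room". Only LA-T then has a cuff, which stays inflated until after skin closure.

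**The concern.** If the only rating is the postoperative one, the patient is not reporting the injection as it happens but remembering it across everything that followed. Ordinary recall error that is the same in both arms would add noise. Here the intervening experience is what was randomised: one arm waits longer and has no cuff, while the other goes sooner into surgery under a cuff. Randomisation balances the patients, but it does not balance what happens to them between injection and rating.

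What is at stake is whether this objective can be read as a statement about the injections. If later surgical or cuff pain raises the remembered injection score in LA-T, two equally painful injections can look different. A WALANT injection that truly hurts more can also look similar, which is the result the plan predicts. If instead the injection seems mild beside cuff pain, the bias runs the other way.

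Nothing planned would repair this. The exploratory timing analysis in SAP Section 9 looks at injection-to-incision time, not at recall. Adjusting for intraoperative pain would not be a clean remedy either, because that score is itself a post-randomisation outcome.

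**Working it through.** **Stated figures.** The documents give no mean, SD, margin or power for infiltration pain, so there is no figure of the plan to reproduce on this point. From SAP Section 9 the check takes only the two means for overall pain, 0.80 and 2.08. The SAP does not label them by arm; I read them as WALANT and LA-T, in line with the primary hypothesis.

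**Step 1: recall delay.** Delay from injection to rating = injection-to-incision time + operative time + time from closure to rating. Taking the last term as equal in the two arms:

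WALANT minus LA-T = (20 − 5) − (LA-T operative time − WALANT operative time) = 15 minutes minus any shortening of surgery with WALANT.

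Protocol Section 3 expects WALANT surgery to be shorter, so 15 minutes is the gap before that offset. It would vanish only if LA-T operations took 15 minutes longer. The documents give no operative times.

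**Step 2: difference in intervening pain.** 2.08 − 0.80 = 1.28 points.

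**Step 3: illustration of bias.** Two quantities are assumed because the documents give neither:
- the share of the 1.28-point gap that leaks into the recalled injection score (0% to 50%);
- the SD of infiltration pain (1.5 to 2.5). The SAP's 1.52 belongs to overall pain.

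Formulas, with 50 per arm and two-sided α = 0.05:
- shift b = leak × 1.28
- SE = SD × √(2/50) = 0.2 × SD
- false-positive rate when true injection pain is equal = 1 − Φ(1.96 − b/SE) + Φ(−1.96 − b/SE)

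Worked example, 25% leak and SD 2.0: b = 0.32, SE = 0.40, b/SE = 0.80. The rate is 1 − Φ(1.16) + Φ(−2.76) = 0.123 + 0.003 = 12.6%.

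| Leak (assumed) | Shift, points | SD 1.5 | SD 2.0 | SD 2.5 |
|---|---|---|---|---|
| 0% | 0 | 5.0% | 5.0% | 5.0% |
| 10% | 0.128 | 7.1% | 6.2% | 5.8% |
| 25% | 0.32 | 18.7% | 12.6% | 9.8% |
| 50% | 0.64 | 56.9% | 36.0% | 24.9% |

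The test is two-sided, so a shift of the same size in the opposite direction gives the same rates.

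**Step 4: masking.** Suppose the WALANT injection truly hurts more by 0.5 SD, and the leak raises the LA-T score. Replace b by (0.5 × SD − b) in the formula. Power is then:

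| Leak (assumed) | SD 1.5 | SD 2.0 | SD 2.5 |
|---|---|---|---|
| 0% | 70.5% | 70.5% | 70.5% |
| 10% | 54.5% | 58.7% | 61.2% |
| 25% | 30.0% | 39.8% | 46.0% |

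Under a contrast effect this table would instead describe the masking of a true LA-T excess.

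Both tables use a normal approximation for a difference in means. The planned test is Mann–Whitney, so they show the order of size rather than exact rates. A rating taken right after injection, before the cuff and the incision, sets the leak to zero by design.

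**The case against.** The strongest reply is that no carry-over has been shown. A reader might infer from the arm differences that the infiltration result is in fact distorted, and distorted in WALANT's favour. The documents do not support that: nothing in them measures carry-over, its sign is open, and the larger percentages above come from the far end of an assumed range. This part of the reply stands.

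It is also true that the documents never say outright when the infiltration score was taken. That it was postoperative only is inferred from the absence of any other collection point. The inference is the natural reading of Section 12, but a rating at injection could have been made and not described.

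A further reply is that the present arrangement has a purpose. Protocol Section 11 has independent blinded assessors collect the scores, and under Protocol Section 4 the surgical and anaesthetic staff know the technique. Because WALANT is injected in a preoperative area and LA-T in the operating room, whoever is present at the injection may know the arm. This is a real cost, but a small one if the patient marks the score alone, because the score is then the patient's own.

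Finally, the outcome is secondary. SAP Section 6 promises cautious interpretation of secondary outcomes and keeps the emphasis on the primary one. That limits the weight of the point but does not remove it, since injection pain has its own objective, hypothesis and test.

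**Conclusion.** The point holds as a weakness of measurement, not as a demonstrated bias. On the plan as written, the infiltration comparison rests on a remembered score, and the arms differ in delay, cuff use and surgical pain between the event and the rating. Bias that differs by arm is possible, its direction is uncertain, and it can create or hide a difference. The assumed scenarios run from no effect at all to a serious one, and the documents do not allow a choice among them.

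Two wider readings should be resisted. The primary outcome is not affected: it concerns pain over the whole operation and is rated immediately after it. The tourniquet score is not affected in this way either: it is collected in LA-T only and summarised without a between-group test.

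This is worth correcting because the correction is cheap. It does not threaten the trial's main conclusion.

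**What to change.** In Protocol Sections 8 and 12, state that the patient marks the infiltration score once, on a separate slip, right after the injection and before cuff inflation, draping or incision in both arms. Keep the postoperative questionnaire for overall pain, tourniquet pain and satisfaction. The patient should complete the slip unprompted and it should be sealed, because the person handing it out may know the arm from the room. The cost is one 0–10 item, with no extra visit or staff and no change to treatment.

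The document is written largely in the past tense and already reports results, so this may come too late for some or all patients. For scores already collected postoperatively, state the rating time, label the outcome 'recalled infiltration pain', limit any conclusion of similarity or difference to recalled pain, and report differential recall as a limitation. If a rating at injection was in fact taken, say so in Sections 8 and 12; the concern then falls away for those patients.

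### The surgical team and its notes are not a stated source for intraoperative complications, so events can be under-counted and a low count misread as safety

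*Combined protocol and SAP*

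**What the plan says.** Protocol Section 3 lists as a secondary objective: "To describe intraoperative complications in each group". Section 8 defines the outcome as "bleeding requiring intervention, nerve injury, or other deviations from normal course". SAP 1 carries it as a secondary endpoint, recorded as yes or no with the type of event.

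Section 12 gives the data sources:
- For complications: "Standardized questionnaire completed postoperatively by the patient and a blinded assessor captured VAS scores, satisfaction, and complications".
- For the notes: "Operative time and tourniquet parameters abstracted from operative notes".

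Section 11 describes the assessors' task as follows: "Outcome assessors (who collected VAS and satisfaction scores) were independent and blinded to group assignment". It does not mention complications. Section 4 has the treating staff unblinded: "Surgeons and anesthetic personnel: aware of technique for safety".

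SAP 6 expects few complications, so it makes the analysis mainly descriptive, with a test only if events suffice. SAP 3 asks for 95% confidence intervals with categorical summaries. No surgeon report form or adverse-event form is described.

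**The concern.** The named source does not fit the outcome. Bleeding that needs control, damage to a nerve in the wound and other departures from the normal course are seen first, and sometimes only, by the people operating. The patient is awake and can report some events, such as an extra injection, but cannot see into the wound. A blinded assessor who takes scores after surgery is not described as being present during it. Section 14 also lists cardiovascular effects of epinephrine among the risks, and the treating team is best placed to notice those too.

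The stake is the safety description. Bleeding is the obvious harm to check when the tourniquet is left out. With few events expected, missing even one or two changes what a reader takes from the table: a zero may reflect the source rather than the procedure. A descriptive analysis does not cure this, because a descriptive count is only as good as its source.

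**Working it through.** **Step 1. Sources side by side.**

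| Item | Stated source (Section 12) | Who is best placed to observe it |
|---|---|---|
| Pain and satisfaction scores | Postoperative questionnaire | Patient |
| Operative time, tourniquet parameters | Operative notes | Surgical team |
| Intraoperative complications | Postoperative questionnaire | Mainly the surgical team |

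The first two rows match source to observer; the third does not. The operative notes are already opened for every patient for another purpose, but complications are not among the items taken from them.

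**Step 2. What under-capture would do (illustration only).** The plan has no figure of its own to reproduce here: it gives neither an expected complication rate nor the share of true events that the questionnaire would pick up. The only input from the documents is the arm size, n = 50 (Section 9). Two quantities are assumed:
- *s*, the share of true events captured, taken as known and set at 100%, 75%, 50% and 25%;
- a true rate *p* of 6% (3 of 50) in the second calculation.

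*Upper limit for the true rate when 0/50 is recorded.* The exact two-sided 95% upper limit for the recorded rate is 1 − 0.025^(1/50) = 0.0711. If only a share s is recorded, the limit for the true rate is 0.0711/s.

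*Chance that no event is recorded in an arm.* This is (1 − p·s)^50. At p = 0.06 it is 0.94^50, 0.955^50, 0.97^50 and 0.985^50 in turn.

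| Assumed capture s | Upper 95% limit for true rate, given 0/50 recorded | Events expected on record at p = 6% (50·p·s) | Chance that none is recorded at p = 6% |
|---|---|---|---|
| 100% | 7.1% | 3.00 | 5% |
| 75% | 9.5% | 2.25 | 10% |
| 50% | 14.2% | 1.50 | 22% |
| 25% | 28.4% | 0.75 | 47% |

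The table shows how a zero loses meaning as capture falls. It is not evidence about what capture was in this trial. No comparison between arms is attempted, because the documents give no arm-specific rates.

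**Step 3. The interval method.** SAP 3 requires 95% intervals but does not name a method. The usual normal-approximation interval at 0/50 has standard error √(0 × 1/50) = 0 and collapses to a point, whereas the exact interval runs from 0% to 7.1%. With few events expected, the choice matters.

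**The case against.** The strongest reply is that Section 12 says who completed the form, not where the information came from. Nothing bars the assessor from asking the surgeon or reading the note. This stands. A reader might infer that the surgeon was excluded as a source, but the documents are only silent on it. If surgeons or notes were in fact used, the source problem is one of wording.

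A reader might also infer that an assessor told of an arm-revealing event, such as an unplanned tourniquet, must either leave it off the form or be unblinded for the primary score. The documents do not support that. They do not give the order of items, and a complication entered after the score cannot change it. The score is also the patient's own rating. In any case, tourniquet pain is a VAS item defined only for LA-T, and Section 12 places VAS scores on this same questionnaire. That item could reveal the arm far more often than a rare complication would.

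A third tempting reading is that the form is always completed while the lidocaine still hides new numbness. SAP 8 places the VAS immediately after surgery, but Section 12 says only that the form is completed postoperatively, and Section 4 follows patients to an early postoperative assessment. Completion in one sitting is not stated.

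Nor do the documents show that under-counting favours WALANT. Equal under-capture shrinks whatever difference exists, and its direction is unknown.

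Finally, arm size alone prevents a firm safety conclusion: 0/50 with perfect recording still allows 7.1%. That is true, but it is no reason to use a source that widens the uncertainty by an unknown amount.

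**Conclusion.** The point holds in a limited form. As written, the plan takes intraoperative complications from people poorly placed to see them, and does not name the team that sees them or the notes that would record them. Events can be under-counted, and a low or zero count could be read as reassurance that it does not give.

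The size cannot be stated from the documents. On assumed capture of 100% down to 25%, the upper limit behind a recorded 0/50 runs from 7.1% to 28.4%; these are illustrations only. The conclusion rests on reading Section 12 as a full list of sources, which is the natural reading but is not stated.

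The outcome is secondary and mainly descriptive, SAP 6 already asks for caution with secondary outcomes, and the primary pain result is not affected. This is an improvement the sponsor could make (COULD), not a defect in the main comparison.

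**What to change.** - **Source.** Abstract complications for all patients from the operative notes, and from anesthetic notes where they exist. State in Section 12 that this item is unblinded.
- **Separation.** Record it apart from, and after, the blinded VAS and satisfaction form, preferably through someone who does not collect those scores.
- **Second source.** Keep the questionnaire item, and show both sources by arm.
- **Reporting.** Give n/N by arm, and specify exact limits for the 95% intervals that SAP 3 already requires, including for 0/N.
- **Completed cases.** Label the work as retrospective re-abstraction, because the SAP already quotes results.
- **If the surgeon or the notes were in fact used.** Correct Section 12 to say so. What then remains is keeping this item separate from the VAS form, and the interval method.

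The cost is one more field in up to 100 operative notes that are already opened for operative time, any anesthetic notes to be read alongside them, and some abstractor time. The downside is that the notes are written by an unblinded surgeon and may omit minor events, which is why both sources should be shown. The primary analysis does not change.

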Subset excluding major deviations (e.g., cross-over of anesthetic technique, incomplete surgery) if any occurred. Primary inferences will be based on ITT; PP will be supportive.

3. General statistical principles

- Two-sided tests with significance level $\alpha = 0.05$.
- Continuous variables: reported as mean \pm SD if approximately normal, or median (IQR) if skewed.
- Categorical variables: counts and percentages with 95% confidence intervals.
- Normality checked with Shapiro–Wilk test and inspection of histograms.
- Main analyses non-parametric where distribution assumptions are not met; parametric tests may be reported as sensitivity analyses.
- Statistical software: SPSS version 29.

4. Baseline characteristics

Baseline demographics and clinical characteristics (age, sex, BMI, ASA class, CTS-6 score) will be summarized by group using descriptive statistics.

- Continuous variables: compared using independent-samples t-test or Mann–Whitney U test as appropriate.
- Categorical variables: compared using chi-square or Fisher’s exact test as appropriate.
These comparisons are descriptive; no p-value adjustment is planned as they are not hypothesis-driven.

5. Primary outcome analysis

Outcome: Overall intraoperative pain VAS (0–10).

- **Primary analysis method:**
Mann–Whitney U test comparing VAS scores between WALANT and LA-T.
- Effect size:
 - Median difference with 95% CI.
 - Non-parametric effect size measure (e.g., rank-biserial correlation) as reported; you previously used effect size ≈ 0.63 with 95% CI.

- **Sensitivity analysis:**
Independent-samples t-test (parametric), assuming approximate normality, to corroborate non-parametric findings.

No adjustment for multiple testing is applied to the primary endpoint.

6. Secondary outcomes analysis

1. Infiltration pain VAS (0–10)

- Analysis: Mann–Whitney U test comparing WALANT vs LA-T.
- Report: medians (IQR), means (SD), p-value, and effect size.

2. Tourniquet pain VAS (LA-T only)

- Descriptive analysis within LA-T arm: median (IQR), distribution plots.
- No between-group statistical test (not defined in WALANT arm).

3. Operative time (minutes)

- Analysis: Mann–Whitney U test for group comparison.
- Report: median (IQR) per group, p-value, effect size.

4. Patient satisfaction (0–10)

- Analysis: Mann–Whitney U test to compare satisfaction scores between groups.
- Report: median (IQR), p-value, and effect size.

5. Intraoperative complications

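### The operative-time comparison ignores surgeon and names no difference in minutes with a confidence interval, so it may lose precision and leaves any time saving without an interval

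*Combined protocol and SAP*

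**What the plan says.** Protocol section 3 states a directional secondary hypothesis: "WALANT will shorten operative time compared with LA-T". Section 8 defines the outcome: "Operative time (minutes): from skin incision to completion of skin closure". Section 7 says who operated: "Two experienced surgeons (orthopedic hand consultant and neurosurgery peripheral nerve specialist) performed all procedures; each performed approximately 50 cases". Section 10 describes the allocation: "Simple computerized randomization with 1:1 allocation to WALANT or LA-T". It mentions no stratification by surgeon or site.

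For this outcome SAP section 6, item 3, plans a "Mann–Whitney U test for group comparison" and then "Report: median (IQR) per group, p-value, effect size". For the primary pain outcome, SAP section 5 goes further and lists "Median difference with 95% CI" under its effect-size heading.

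Surgeon appears in SAP section 7 as a pre-specified subgroup, but the within-stratum and interaction tests there concern intraoperative pain. SAP section 9 lists plots of operative time and subgroup plots by surgeon, without saying which outcome the subgroup plots show.

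**The concern.** Incision-to-closure time depends directly on how fast the surgeon works. When two surgeons are pooled in one two-sample test, any difference in their usual pace is added to the noise against which the technique is judged. Surgeon is known for every case and the plan already uses it for pain, so that noise could be removed at almost no cost.

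The second part concerns reporting. A hypothesis that one technique is quicker is useful only if the reader learns how many minutes are saved and how precisely. The operative-time item names neither a between-arm difference nor a confidence interval. At stake are a real time difference that may be missed, and a detected one whose size comes without an interval.

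**Working it through.** **Figures in the plan.** There is none to reproduce. The only power statement in the documents (about 94%) concerns pain. No SD, expected effect or between-surgeon gap is given for operative time, so those are assumptions below.

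**Inputs from the documents.** 100 patients, 50 per arm; two surgeons with about 50 cases each; two-sided α = 0.05; allocation not stated to be stratified by surgeon.

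**Assumptions.** Within-surgeon times are normal with SD 1 (all quantities in within-surgeon SDs). The technique effect is δ = 0.57, chosen to give about 80% power when the surgeons do not differ. The surgeon gap g ranges from 0 to 2 and has the same size in both arms.

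**Step 1: variance.** With half the cases from each surgeon, pooling adds 0.5 × 0.5 × g² = g²/4, so the pooled variance is 1 + g²/4. This is 1.06 at g = 0.5, 1.25 at 1, 1.56 at 1.5 and 2.00 at 2.

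**Step 2: approximate power of the pooled test.** Under normality the Mann–Whitney test has relative efficiency 3/π = 0.955, so the effective n per arm is 50 × 0.955 = 47.7.

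Power ≈ Φ(δ / [√(1 + g²/4) × √(2/47.7)] − 1.96).

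At g = 0: 0.57/0.2047 = 2.785, and Φ(0.825) = 79.5%. At g = 1: 2.785/1.118 = 2.491, and Φ(0.531) = 70.2%. At g = 2: 2.785/1.414 = 1.969, and Φ(0.009) = 50.4%.

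**Step 3: simulation.** 6,000 trials per setting, 50 per arm and 50 per surgeon, allocation ignoring surgeon. The pooled Mann–Whitney test is compared with the van Elteren test stratified by surgeon. Monte Carlo standard error is about 0.5 to 0.6 points for the power figures.

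| Surgeon gap (SD) | Pooled Mann–Whitney | Stratified by surgeon | Loss (points) |
|---|---|---|---|
| 0 | 78.7% | 78.0% | −1 |
| 0.5 | 76.8% | 78.7% | 2 |
| 1 | 69.2% | 78.5% | 9 |
| 1.5 | 57.6% | 76.9% | 19 |
| 2 | 45.9% | 77.5% | 32 |

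A second simulation (4,000 trials per setting, δ = 0.566) compared the pooled test with a linear model on arm and surgeon. It gave 77% against 79% at g = 0, 67% against 78% at 1, 56% against 78% at 1.5, and 45% against 79% at 2.

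**Step 4: validity.** With no technique effect, the pooled test rejects in 4.5% to 5.2% of trials across all gaps.

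**Step 5: chance imbalance.** The between-arm difference in the share of cases from one surgeon has SD 0.10, so it typically moves a crude mean difference by 0.1g. A 20/30 split or worse within an arm has probability about 7%; a 20/30 split moves the mean difference by (30 − 20)/50 × g = 0.2g. This is not a further loss. The pooled variance of a mean difference is (2/50)(1 + g²/4) = 0.04 + 0.01g², and 0.01g² = (0.1g)² is the imbalance term, so the power figures already contain it.

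**Step 6: what an interval would show.** With no surgeon gap, the approximate 95% half-width of a rank-based shift estimate is 1.96 × SD × √(2/50) × √(π/3). For assumed SDs of 3, 5 and 8 minutes this is 1.2, 2.0 and 3.2 minutes. Arm medians and a p-value do not convey this precision.

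**The case against.** The strongest case against the point has four parts.

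*The surgeon gap is assumed.* This stands. A reader might infer that surgeon variation masks the technique effect. The documents do not support that: both operators are described as experienced, both arms have a mini-open release through the same size of incision, and different specialties do not establish different speeds. Up to 0.5 SD the loss is negligible, and the large losses need gaps of 1.5 to 2 SD, for which the documents give no evidence.

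*Imbalance of surgeons between arms is not bias.* This also stands. Allocation is random, so chance imbalance is ordinary sampling error, and type I error stays near 5%.

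*The effect is estimated.* A reader might infer that its size is never estimated. That goes too far: two medians in minutes allow a crude subtraction, and the effect size in item 3 could be read in the light of SAP section 5, where that heading covers a median difference with an interval. But the same heading also covers a unit-free rank measure, so the term alone does not secure minutes. SAP section 3 promises confidence intervals only for categorical variables. Nor does the Mann–Whitney test, in general, test the difference between two medians.

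*Other material may help, and this is only a secondary outcome.* SAP section 3 allows parametric sensitivity analyses and SAP section 9 lists plots by surgeon, but neither is a surgeon-adjusted analysis. The SAP says that secondary outcomes are interpreted cautiously and claims no power for operative time. That lowers the severity, but supplies neither an estimate nor an interval.

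**Conclusion.** The point holds as a possible loss of precision and a gap in reporting; it does not make the planned test invalid. Two facts come from the text alone: the operative-time analysis takes no account of surgeon, and it names no between-arm difference in minutes with a 95% CI.

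The size of the power loss is conditional. For an assumed effect of 0.57 within-surgeon SD, normal times and equal caseloads, it is 0 to 2 points at gaps up to 0.5 SD, about 10 at 1 SD, about 20 at 1.5 SD and about 30 at 2 SD. Adjustment costs almost nothing when the surgeons do not differ, so the case for it does not depend on knowing the gap. Severity is minor to moderate.

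**What to change.** Add to SAP section 6, item 3, a linear model of operative time in minutes on arm and surgeon, with robust standard errors, reporting the adjusted difference in minutes with its 95% CI. If a rank method is preferred, use the van Elteren test with a Hodges–Lehmann difference and interval that are also stratified by surgeon, so that test and interval correspond. Fix the scale in advance: a switch to log time after checking skewness would make the model depend on the data and would give a ratio where minutes are wanted. Show medians by arm and surgeon.

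Keep the planned Mann–Whitney test beside the addition. The documents already quote observed pain results, so if operative-time data have also been seen, label the adjusted analysis as post hoc.

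The cost is a few lines of SAP text, one extra model and one degree of freedom. No new data are needed, because the surgeon subgroup in SAP section 7 already relies on knowing who operated.
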